9.2 Dose Escalation Procedures and Stopping Criteria

9.2.1 Dose Escalation Procedures (Part 1)

Following completion of each cohort, a summary of all relevant safety data (AEs, vital signs, 12-Lead ECG and laboratory safety tests) and PK data (Cmax, Tmax, AUC0-24, AUC0-t, AUC0- ∞ and t½) up to Day 3 (48 hours post dose) will be produced on behalf of the Chief Investigator. Planned doses may be modified following a review of emerging data. Progression to the next dose level and dose selection will be based on the available safety and PK data from at least 5 subjects from the preceding dose level. If fewer than 5 evaluable subjects are obtained then additional subjects must be dosed for that cohort prior to considering dose escalation. If it is not appropriate to escalate the dose according to the proposed dose escalation schedule, then the same dose, an intermediate dose or a lower dose may be given following discussion between the Sponsor and the Investigator. If the dose escalation stopping criteria in section 9.2.3 are met, then the dose level that was tested will

GB-HV-01 Clinical Study Protocol
RD 676/25641 Version: FINAL 6.0 / 05 April 2016 Page 30 of 73

not be repeated or exceeded, however a lower dose may be given following discussion between the Sponsor and the Investigator.

The members of the dose escalation review committee will consist of (chair and voting member), (voting member) and (PK, non voting member). Both voting safety committee members must participate in all meetings or provide an acceptable designee if unavailable.

There will be a Telephone Conference at a pre-appointed time to involve the Simbec Trial manager and Investigator (or their deputies) and the Sponsor's representative(s). After discussion of all the data, the decision will be made to dose escalate and a written document signed by the Investigator (or deputy) and Sponsor will be produced ratifying that decision. Recommendations to continue the study will require unanimous consent from the 2 voting members. In the event that unexpected safety issues are observed that are beyond the expertise of committee members, additional committee members or ad hoc committee members may be added to the safety committee. In the event that there is not a unanimous decision among the 2 voting members, an independent arbiter will be appointed to resolve the disagreement. Full minutes, to be agreed by all parties, will be produced for each discussion regarding dose escalation and filed in the Investigator Site File (ISF). A copy will be provided to the Simbec Pharmacist and this will allow the Investigational Medicinal Product (IMP) to be assembled for the next dose level prior to the performance of the next stage of the protocol.

The continuation of the study will be dependent upon the accrual of acceptable safety data following each cohort as indicated by the signature of each safety summary by the Chief Investigator or delegate and by the Sponsor.

Please see Section 9.2.3 for dose escalation stopping criteria.

9.2.2 Dose Decision and Review Procedures (Part 2)

Dose Selection for Part 2:

The dose of TD139 to be administered in Part 2 will be 3mg, based on data from Part 1 (single doses up to 10mg) and on pre-clinical efficacy and safety data. The highest acceptable dose level in Part 1 of the study will not be exceeded in Part 2.

Ongoing Safety Review:

Part 2 will be discontinued at any time if any unacceptable safety findings are identified (see Study Stopping Criteria in section 9.2.3).

Formal Interim Review:

During **Part 2** there will be an interim review by a safety committee after 8 subjects have been dosed to review the available blinded safety and PK data. The initial 8 subjects will be randomised in such a way that 5 will receive TD139 and 3 will receive placebo. Following a review of this data a decision will made as to whether to randomise up to 4 further subjects (where 3 subjects will receive TD139 and 1 will receive placebo). The dose and PK sampling times may also be modified following a review of the data.

The following will be reviewed at the interim review meeting:

Clinical Study Protocol

RD 676/25641 Version: FINAL 6.0 / 05 April 2016 Page 31 of 73

• A summary of all relevant safety data from at least 7 out of 8 subjects (AEs, vital signs, 12-Lead ECG, spirometry and laboratory safety tests),

- PK data from at least 7 out of 8 subjects (Cmax, Tmax, AUC_{0- τ}, AUC0-t, AUC0- ∞ and $t^{1/2}$)
- BAL data: At least 7 out of 8 subjects will have completed both of the following:
 - o paired BAL samples
 - o adequate BAL macrophage cell yields (absolute minimum macrophage numbers = 4 million)

The data will be compiled by Simbec on behalf of the Chief Investigator once the first 8 subjects have been dosed. Subsequent interim review meetings will take place as detailed in **Table S1**. Each site will be required to scan the applicable CRF pages and transfer the required safety data needed to Simbec data management in order for the data to be consolidated from each site. PK samples will be shipped to Simbec for assaying and subsequent PK analysis. A summary of all of the available data will be provided to all the safety committee for review.

The members of the safety committee will consist of _______ (joint chair and voting member), ______ (joint chair and voting member), ______ (joint chair and voting member) and ______ (voting member). All 5 voting safety committee members must participate in all meetings or provide an acceptable designee if unavailable.

There will be a Telephone Conference at a pre-appointed time to involve all of the safety committee members. After discussion of all the data, the decision will be made as to whether to randomise up to 4 further subjects in Cohort 1 or move on to a second dose level in Cohort 2 (see Table S1). It will also be decided whether the dose and PK sampling times will also be modified. Recommendations to continue/discontinue/amend the study will require unanimous consent from the 5 voting members. In the event that unexpected safety issues are observed that are beyond the expertise of committee members, additional committee members or ad hoc committee members may be added to the safety committee. In the event that there is not a unanimous decision among the 5 voting members, an independent arbiter will be appointed to resolve the disagreement.

A written document signed by each site Investigator (or deputy) and Sponsor will be produced ratifying that decision. Full minutes, to be agreed by all parties, will be produced for each discussion regarding dose escalation and filed in the Investigator Site File (ISF). A copy will be provided to the Simbec Pharmacist and this will allow the Investigational Medicinal Product (IMP) to be assembled accordingly for each site. The procedure for the ongoing and interim data review in Part 2 will be fully documented to a dose review manual. The manual will be approved by the sponsor and all clinical site Investigators prior to the start of the trial.

Please see Section 9.2.3 for study stopping criteria.

9.2.3 Study Stopping Criteria

Part 1:

GB-HV-01 Clinical Study Protocol
RD 676/25641 Version: FINAL 6.0 / 05 April 2016 Page 32 of 73

• Dose Escalation will stop if 3 or more subjects in a cohort experience the same moderate adverse event that is deemed possibly, probably or definitely related to IMP treatment.

- Dose Escalation will stop if 1 or more subjects in a cohort experience severe adverse event that is deemed possibly, probably or definitely related to IMP treatment.
- Dose escalation would stop if 1 or more than 1 subject in the cohort experience a drug related SAE or a clinically significant drug-related non-SAE.
- Dose escalation will stop if the C_{max} and/or AUC values in each cohort reach or exceed those observed in the dog following 9.1 mg/kg/day 14 day repeat dosing, equating to a gender-averaged AUC(0-t) of 2450 ng*hr/mL and Cmax of 558 ng/mL on Day 14.

Part 2:

- The study will be stopped if 3 or more subjects experience the same moderate adverse event
- The study will be stopped if 2 or more subjects experience a severe adverse event.
- The study will be stopped if 1 subject experiences a drug related SAE or a clinically significant drug-related non-SAE.
- The study will be stopped if the Cmax and/or AUC values reach or exceed those observed in the dog following 9.1 mg/kg/day 14 day dosing, equating to gender-averaged AUC(0-t) of 2450 ng*hr/mL and Cmax of 558 ng/mL on Day 14.

During the clinical conduct of the study, all Investigators will be required to immediately inform the Chief Investigator, the sponsor and Simbec of any moderate, severe, SAE or clinically significant non-SAE. This notification is required in order to allow coordination of information and assessment on whether the stopping criteria has been met.

The procedure for the ongoing and interim data review in Part 2 will be fully documented to a dose review manual, approved by all parties.

The study will be discontinued if any unacceptable safety findings are identified. The Chief Investigator, Principal Investigators and the Sponsor will make this decision jointly. A written document signed by the Investigator (or deputy) and Sponsor will be produced ratifying the decision.

Please see Section 9.4.3 for possible reasons for discontinuation of an individual subject.

9.3 Discussion of Study Design, including the choice of Control Groups and Dose Leaders

This study will be divided into 2 parts. **Part 1** is a randomised, double-blind, single centre, placebo-controlled, SAD, phase I study designed to assess the safety, tolerability, PK and PD of TD139 in up to 36 healthy male subjects.

Part 1 of this study employs a single ascending dose design; corresponding placebo control will be administered in order to evaluate treatment-related effects.

The design of **Part 1** of this study is typical of that used for FIM studies with a "dose leader" design for built-in safety. A dose leader design will be implemented in which 2 subjects (1

GB-HV-01 Clinical Study Protocol

RD 676/25641 Version: FINAL 6.0 / 05 April 2016 Page 33 of 73

TD139 and 1 placebo) in each cohort will be dosed approximately 24 hours before the rest of the Cohort. Providing there have been no safety concerns in the dose leader group up to the 24 hour time point, the remainder of the cohort (4 subjects) will be dosed a day later and will be randomised in such a way that one further subject receives placebo. This design allows maintenance of the "blind".

Safety and PK data from a minimum of 5 subjects of each cohort will be required for data review prior to dose escalation.

Part 2 will be a randomised, double-blind, multi-centre, placebo-controlled, multiple dose expansion cohort study designed to assess the safety, tolerability, PK and PD of TD139 in up to 24 male and female subjects of non child-bearing potential with IPF.

This part of the study will consist of 1 cohort of up to 24 IPF subjects, who will receive a single dose of TD139 or placebo via DPI once daily for 14 days (TD139 and placebo dosed according to **Table S1**). The initial dose level used will be 3mg based on PK and safety data from **Part 1** and on pre-clinical efficacy and safety data.

During **Part 2** there will be an interim review by the safety committee after 8 subjects have been dosed to review the available blinded safety and PK data. The initial 8 subjects will be randomised in such a way that 5 will receive TD139 and 3 will receive placebo. Following a review of this data a decision will made as to whether to randomise up to 4 further subjects (where 3 subjects will receive TD139 and 1 will receive placebo) in Cohort 1 or move on to a second dose level in Cohort 2 (see Table S1). The dose and PK sampling times may also be modified following a review of the data.

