9.7.1.4.1 Adverse Events

AEs and serious adverse events (SAEs) that occurred during the study along with their severity and relationship to study drug will be reported.

An AE is defined as:

Any untoward medical occurrence in a patient or clinical study subject administered a medicinal product and which does not necessarily have a causal relationship with this treatment.

An unexpected adverse reaction is defined as:

An adverse reaction, the nature, or severity of which is not consistent with the applicable product information (e.g. investigator's brochure for an unapproved investigational product or summary of product characteristics (SmPC) for an authorized product)

AEs will be monitored throughout the study from the first dose through to the follow-up post study visit. All AEs should be recorded, whether considered minor or serious, drug-related or not.

All abnormal laboratory findings considered to be clinically significant must be recorded as AEs.

Recording of Adverse Events

All of the following details should be recorded in the subject's CRF for each AE:

- Full description of AE.
- Date and time of onset.
- Date and time of resolution.
- Severity of event, to be assessed by the investigating physician in accordance with the definitions below.
- Relationship to IMP to be assessed by the investigating physician in accordance with the definitions below.
- Action taken (if any).
- Outcome and details of any further follow-up.

Grades of Adverse Event Severity

The following grades should be used by the investigating physician to describe the severity of AEs.

The following are the only grades which should be used to describe AE severity. Only 1 severity grade should be used for each AE (e.g. mild - moderate is not acceptable).

GB-HV-01 Clinical Study Protocol Confidential RD 676/25641 Version: FINAL 6.0 / 05 April 2016 Page 53 of 73

SEVERITY OF THE AE	DEFINITION
Mild AE	The AE does not interfere with the subject's daily routines. It causes no more than slight discomfort
Moderate AE	The AE interferes with some aspects of the subject's daily routines.
Severe AE	The AE causes inability to carry out the subject's daily routine.

Definitions of Adverse Event Causality

The following definitions should be used by the investigating physician to describe the relationship between an AE and the IMP.

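### Read literally, Part 2 stopping criteria 1 and 2 stop the study for three moderate cases of an event but not for two moderate cases and one severe case

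*Protocol*

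**What the plan says.** Section 9.2.3 of the protocol lists the Part 2 stopping criteria. Three of them concern adverse events:

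- Criterion 1: "The study will be stopped if 3 or more subjects experience the same moderate adverse event".
- Criterion 2: "The study will be stopped if 2 or more subjects experience a severe adverse event".
- Criterion 3: "The study will be stopped if 1 subject experiences a drug related SAE or a clinically significant drug-related non-SAE".

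Criteria 1 and 2 carry no relatedness condition, and criterion 1 has no wording such as 'or worse'. Criterion 4 concerns drug exposure and plays no part here.

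Section 9.7.1.4.1 defines mild, moderate and severe separately and adds: "Only 1 severity grade should be used for each AE". It does not say how a severe case counts towards a threshold expressed in moderate cases.

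For Part 1, the matching severe-event rule has a threshold of one: "Dose Escalation will stop if 1 or more subjects in a cohort experience severe adverse event that is deemed possibly, probably or definitely related" to treatment.

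Section 9.2.3 also requires immediate notification of moderate, severe and serious events, with this purpose: "This notification is required in order to allow coordination of information and assessment on whether the stopping criteria has been met". A general clause follows: "The study will be discontinued if any unacceptable safety findings are identified". Section 9.2.2 sets the rule for interim reviews: "Recommendations to continue/discontinue/amend the study will require unanimous consent from the 5 voting members". Both sections refer to a dose review manual, which is not among the documents at hand.

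**The concern.** A set of count rules for safety should be ordered by severity: if a pattern of cases stops the study, the same pattern with one case made worse should stop it too. Criteria 1 and 2 break this. Criterion 1 counts moderate cases and criterion 2 needs two severe ones. Upgrading one of three moderate cases therefore takes a case away from the first count without completing the second.

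In the worse pattern, stopping then depends on a causality call under criterion 3 or on judgement. Criteria 1 and 2 need neither. Part 1 has no such gap for related events, because one related severe event is enough. The gap opens in Part 2 because the severe threshold is two while the moderate criterion still names only moderate events.

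**Working it through.** The plan gives no operating characteristics for these rules, and Section 9.9.2 reports no formal sample size calculation, so there is no stated figure to reproduce.

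**Step 1: which counts escape.** For one event, let m be the number of subjects with it graded moderate and v the number with it graded severe. Part 2 has at most 24 subjects.

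Criteria 1 and 2 stop the study if m ≥ 3 or v ≥ 2. Neither is met only if m ≤ 2 and v ≤ 1. With m + v ≥ 3, that leaves one pair: m = 2, v = 1. For three cases in all:

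| Moderate | Severe | Criterion 1 or 2 met? |
|---|---|---|
| 3 | 0 | Yes (criterion 1) |
| 2 | 1 | No |
| 1 | 2 | Yes (criterion 2) |
| 0 | 3 | Yes (criterion 2) |

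Enumeration for 8, 12 and 24 subjects gives the same single pair. Under the Part 1 thresholds (m ≥ 3 or v ≥ 1, related events), escape needs m ≤ 2 and v = 0, so no count of three or more escapes.

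**Step 2: how often one event term ends there.** The protocol gives no rates. Assume that each of 24 subjects independently has the event at moderate or severe grade with probability p, and that a share s of cases is severe. Then

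U = C(24,2) × 22 × (p(1−s))² × (ps) × (1−p)²¹, where C(24,2) × 22 = 276 × 22 = 6072.

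- p = 0.05, s = 0.1: 6072 × 0.045² × 0.005 × 0.95²¹ = 0.0209
- p = 0.10, s = 0.2: 6072 × 0.08² × 0.02 × 0.90²¹ = 0.0850
- p = 0.125, s = 1/3: 6072 × 0.0833² × 0.0417 × 0.875²¹ = 0.1064

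Over p from 0.05 to 0.20 and s from 0.1 to 1/3, the first and last of these are the minimum and maximum.

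**Step 3: allow for the other count-based stops.** Let r be the probability that a case meets criterion 3. Let q be the probability that each of the 23 subjects other than the severe case has some other severe event, which would meet criterion 2. Taking these as independent,

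Net = U × (1−r)³ × (1−q)²³.

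- Highest: r = 0.3, q = 0.02: 0.1064 × 0.343 × 0.628 = 0.0229
- Lowest: r = 0.5, q = 0.05: 0.0209 × 0.125 × 0.307 = 0.0008

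**Step 4: severe cases more likely to meet criterion 3.** Let a severe case meet it with probability 0.8 and a moderate case with probability rₘ. The factor (1−r)³ becomes (1−rₘ)² × 0.2.

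- Highest: rₘ = 0.3, q = 0.02: 0.1064 × 0.098 × 0.628 = 0.0066
- Lowest: rₘ = 0.5, q = 0.05: 0.0209 × 0.05 × 0.307 = 0.0003

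**Step 5: effect of counting severe cases in criterion 1.** The rule becomes m + v ≥ 3 or v ≥ 2, and only (2, 1) changes. With 24 subjects and criteria 1 and 2 alone, the assumed per-subject risks give these chances of stopping for one event term:

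| Moderate risk | Severe risk | As written | Reworded | Difference |
|---|---|---|---|---|
| 5% | 1% | 0.138 | 0.179 | 0.041 |
| 10% | 2% | 0.486 | 0.569 | 0.083 |
| 20% | 5% | 0.932 | 0.961 | 0.029 |

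**The case against.** The literal reading is not forced. The one-grade sentence in Section 9.7.1.4.1 is a recording rule aimed at hybrid grades, not a counting rule. By the protocol's own definitions, an event that prevents the daily routine also interferes with parts of it, so a safety committee could reasonably count a severe case as at least moderate. This stands as a possible reading. If it is the intended one, the rewording merely records it. Four sites report into this rule, so it should be readable in only one way.

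The other provisions also reach this state. A drug-related event that stops someone's daily routine would normally be judged clinically significant and so meet criterion 3. Every moderate or severe event is notified at once, an interim recommendation to continue needs five votes or an arbiter, and the general clause allows a stop at any time. All of this narrows the practical gap, but none of it repairs the count rule: criterion 3 needs a causality call and the rest need judgement.

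The unseen dose review manual may settle how grades are counted. That cannot be excluded.

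The probabilities rest entirely on assumptions, and the top of the net range is generous. It pairs a 4.2% severe risk for one event term (0.125 × 1/3) with only 2% for all other severe events. It also ignores stops triggered by other event terms. The numbers are therefore illustrative only, but the break in ordering does not depend on them.

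Finally, criteria 1 and 2 already stop for unrelated events, in patients who each have two bronchoscopies, and the rewording adds some such stops. That is a real cost, though a small one.

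**Conclusion.** The concern holds as a narrow, low-priority defect in a stated safety rule. Read literally, criteria 1 and 2 stop for three moderate cases and not for two moderate cases plus one severe, and no other count of three or more behaves this way.

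It bites only when no other subject has a severe event, none of the cases meets criterion 3, and the severe case was not already counted as moderate. What is left is mainly events judged not drug-related.

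Per event term and under the assumed, independent rates above, the chance of ending Part 2 in this state is 2.1% to 10.6% before the other count-based stops and 0.1% to 2.3% after them. It falls to 0.03% to 0.7% if a severe case meets criterion 3 with probability 0.8. Confidence is medium, because the reading is open to argument and the manual is not shown.

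**What to change.** In Section 9.2.3, let Part 2 criterion 1 count three or more subjects with *the same adverse event of moderate or greater severity*. Leave criteria 2 to 4 as they are, and check that the dose review manual counts grades in the same way.

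The change acts only when an event reaches two moderate cases and one severe. It adds a stop where the count would have stayed there, and brings the stop forward where a later case would have met criterion 1 or 2. The price is a slightly higher chance of stopping, mainly for events judged not drug-related.

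It needs no extra patients, procedures or analyses, but it does need a protocol amendment. Because it alters a stopping criterion, it may well count as substantial under Section 10.2 and then need ethics committee and regulator approval before use. It is best combined with another amendment. A counting note in the dose review manual would be a lighter interim step, but the threshold itself is set in the protocol and should be clear there.

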9.4 Selection of Study Population

Up to 36 healthy male subjects will be required to complete **Part 1** of the study. The subjects will be selected from a large panel who have offered their services as volunteers to Simbec for the purpose of undertaking REC and Regulatory Authority-approved studies on drug safety, absorption and disposition.

Part 1 of the study is to be conducted in healthy subjects and therefore participants are not expected to derive any therapeutic benefit from taking part. TD139 has not been previously administered to humans; therefore its effects in humans are as yet unknown. A healthy subject population with carefully considered inclusion/exclusion criteria will avoid the potential for interaction of TD139 with any underlying disease state or concomitant medication that it may be necessary for patients to take, while ensuring that subjects are fit and well enough for participation in the study.

Up to 24 male and female subjects of non child-bearing potential with a confirmed diagnosis of IPF will participate in **Part 2** of this study. Eligible subjects will be identified at 4 NHS centres (Royal Brompton Hospital, Edinburgh University Hospital, Royal Victoria Infirmary and Royal Devon and Exeter Hospital).

This clinical study can fulfil its objectives only if appropriate subjects are enrolled. The following eligibility criteria are designed to select subjects for whom protocol treatment and procedures are considered appropriate. All relevant medical and non-medical conditions should be taken into consideration when deciding whether this protocol is suitable for a particular subject.

Version: FINAL 6.0 / 05 April 2016

GB-HV-01 Clinical Study Protocol

Page 34 of 73

